3.1.2 Intervention Phase

The intervention to be tested is fluid resuscitation with LR compared to the “usual practice” control fluid of NS. Other than prescribing which crystalloid fluid to use, the intervention will be purposely implemented without intense efforts to standardize timing and volume of fluid resuscitation or other components of clinical care.

The proposed interventional plan is that, prior to receipt of >40 mL/kg of crystalloid bolus fluid, eligible patients will be randomized to receive either NS or LR for all remaining fluid administration (bolus and maintenance) for up to 48 hours. The study period will end at 11:59pm on the calendar day following randomization such that all patients receive at least 24 hours of study fluid, which is the time-window from presentation in which most fluid resuscitation is completed for septic shock.²⁷ This time point for terminating the intervention phase was selected because it provided a pragmatic endpoint that can be used by clinicians to signal the point at which to cease study fluid administration. Selective fluid administration has been previously shown to result in widely different amounts of saline use,⁴⁷ though application of these findings in adults using a different allocation strategy to the one proposed for our study is not clear. Study fluids will not be blinded due to costs and interventions that are not in keeping with a simple, pragmatic trial and based on results from the previously published SPLIT fluid trial in which two-thirds of clinicians correctly

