5.4 Safety Evaluation

This pilot study will not be powered to determine safety. However, the following safety outcomes planned for use in a subsequent large pragmatic trial will be measured if ascertained as part of routine clinical practice:

- Hyperlactatemia, measured as at least one venous or arterial blood lactate measurement >4 mmol/L within four calendar days of randomization
- Hyperkalemia, measured as at least one venous or arterial blood potassium measurement >6 mEq/L (without hemolysis) within four calendar days of randomization
- Hypercalcemia, measured as at least one venous or arterial blood ionized calcium measurement of >1.35 mEq/L or total calcium >12 mEq/L within four calendar days of randomization

- Hypernatremia, measured as at least one venous, arterial, or capillary blood sodium measurement of >155 mEq/L within four calendar days of randomization
- Hyponatremia, measured as at least one venous, arterial, or capillary blood sodium measurement of <128 mEq/L within four calendar days of randomization
- Hyperchloremia, measured as at least one venous, arterial, or capillary blood chloride measurement of >110 mEq/L within four calendar days of randomization
- Clotting of intravenous line in patients who received both ceftriaxone and LR, within four calendar days of randomization
- Therapy for brain herniation, measured as treatment with hyperosmolar therapy (hypertonic saline and/or mannitol) for radiographic and clinical determination of new impending or present brain herniation (but not including a presumptive clinical diagnosis of brain herniation that is disproven by subsequent radiographic studies) within four calendar days of randomization
- Therapy for thromboembolism, measured as radiographic or clinical determination of new venous or arterial thromboembolism requiring initiation of therapeutic anticoagulation for the purposes of treating thromboembolism, within seven calendar days of randomization

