6.3.4 Safety Analysis

Safety endpoints will be tracked between groups as part of this pilot study, but no formal statistical comparisons will be undertaken due to insufficient statistical power. As part of our secondary feasibility analysis, however, we will determine the proportion of patients with complete data available for each safety endpoint listed in Section 5.5 to ensure that it is indeed feasible to capture the safety outcome measures planned for a subsequent large multicenter trial. Specifically, we will track laboratory testing performed as part of routine clinical practice in order to determine the frequency that laboratory results are available for the specified safety outcome measures listed in Section 5.4. It is notable that routine clinical practice for sepsis includes frequent (i.e., daily or more) measurement of blood lactate, sodium, potassium, chloride, and calcium.

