7.1.2 Labeling

Only FDA-approved hospital-issued fluids will be used for this study. The current supply of fluids used at CHOP to be included in this study is NS manufactured by Baxter Healthcare Corporation and LR manufactured by Baxter Healthcare Corporation. Both NS and LR will be labeled as per their existing labels that are in current use as part of routine clinical practice. NS is labeled as “0.9% Sodium Chloride Injection USP” and LR is labeled as “Lactated Ringer’s Injection USP” as part of routine clinical practice. Although an IND will be sought for this study for the purposes of EFIC, since only FDA-approved study fluids that are used as part of routine clinical care for pediatric septic shock (as well as other indications) will be used for this study, no additional labeling will be applied to bags of either NS or LR for the purposes of this study. At CHOP, while NS remains the most common fluid to treat pediatric septic shock in the ED, 50% of the resuscitation fluids used to treat children with septic shock in the pediatric intensive care unit are NS and 50% are LR. Given both NS and LR are commonly used in routine clinical practice and both are FDA-approved, application of study-specific labeling can only contribute to medication errors by altering routine clinical practice. Given the pragmatic nature of the proposed study design that is required to expand this work to the larger PEARN network, enroll several thousand patients, and optimize external validity, it is not practical to employ a dedicated study team to guard against medication errors that may ensue by introducing a non-standardized label on FDA-approved, hospital-issued fluids to be used in this study.

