If AEs are identified, the AE will be reported as they arise as described in Section 8.5 and then will be followed through to resolution or hospital discharge, whichever comes first. In addition, we will also monitor for the specific safety endpoints noted in Section 5.4 that we have *a priori* identified as potential events that may be differentially impacted by use of NS or LR. These safety endpoints will be ascertained through intermittent data collection throughout the intervention and follow-up phases and at hospital discharge or 90 days following randomization, whichever comes first.

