8.5.1 Reporting procedures

AEs will only be reported if judged by the investigators to be related to administration of study fluid. SAEs will be reported regardless of whether these are judged to be related to administration of study fluid. See “Adverse Event Reporting” in Appendix 3 for a flow diagram outlining the need for and timing of reporting of AEs and SAEs.

AEs and SAEs to be collected for subjects enrolled in this study are listed in Table 3, along with classification as either expected within the study population of pediatric patients with septic shock or unexpected. All of the events lists in Table 3 could potentially be related to the study fluid intervention, though this determination will be made on a case-by-case basis. Other unexpected events not listed in Table 3 will not be collected unless the clinical care team and/or the study investigators determine that the event may be related to the study fluid intervention.

Table 3: Adverse Events To Be Collected

Event	AE or SAE	Expected in Pediatric Sepsis
Death ¹	SAE	Expected
Cardiac arrest requiring CPR	SAE	Expected
Arrhythmia requiring intervention	AE	Not Expected
Vasoactive infusion	SAE	Expected
Extracorporeal membrane oxygenation (ECMO)	SAE	Expected
Invasive mechanical ventilation	SAE	Expected
Non-invasive mechanical ventilation	AE	Expected
Dialysis (not pre-existing) ¹	SAE	Expected
Liver dysfunction	SAE	Expected
Limb necrosis	SAE	Expected
Brain herniation ²	SAE	Not Expected
Seizure	AE	Not Expected
Pulmonary embolus	SAE	Not Expected
Deep venous thrombosis	AE	Expected
Central venous line clot requiring pharmacologic therapy ²	AE	Expected
Bleeding (not requiring massive transfusion protocol)	AE	Expected
Bleeding (requiring massive transfusion protocol)	SAE	Not Expected

Hospital-acquired infection ³	AE	Expected
Pressure ulcer	AE	Expected
IV infiltrate (grade 3 or 4)	AE	Expected
Rash	AE	Expected
Hyperlacatatemia > 4 mmol/L ²	AE	Expected
Hyperkalemia >6 mEq/L ²	AE	Not Expected
Hypercalcemia (ionized calcium > 1.35 mEq/L or total calcium > 12 mEq/L) ²	AE	Not Expected
Hypernatremia >155 mEq/L ²	AE	Not Expected
Hyponatremia <128 mEq/L ²	AE	Not Expected
Hyperchloremia >110 mEq/L ²	AE	Expected

¹Event also included as pre-specified efficacy outcome

²Event also included as pre-specified adverse outcome

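### The line-clotting safety outcome requires receipt of LR, so its counts are not comparable between arms and lean toward LR even when the true clot risk is equal.

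*Combined protocol and SAP*

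**What the plan says.** Section 5.4 lists the safety outcomes to be measured when routine care reveals them. One of them is "Clotting of intravenous line in patients who received both ceftriaxone and LR, within four calendar days of randomization". No other item in that list depends on which study fluid the child received. The section introduces the list as "safety outcomes planned for use in a subsequent large pragmatic trial".

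Section 6.3.4 states: "Safety endpoints will be tracked between groups as part of this pilot study, but no formal statistical comparisons will be undertaken". It adds that the share of patients with complete data will be determined for each safety endpoint. Section 8.1 describes the Section 5.4 endpoints as "potential events that may be differentially impacted by use of NS or LR".

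On timing, Section 3.1.2 says: "The study period will end at 11:59pm on the calendar day following randomization". Under Section 3.1.3, the clinicians choose any later fluid. Section 7.1.2 says that at this hospital "50% of the resuscitation fluids used to treat children with septic shock in the pediatric intensive care unit are NS and 50% are LR".

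Table 3 in Section 8.5.1 has a row for "Central venous line clot requiring pharmacologic therapy". It carries no fluid condition, and its footnote 2 marks it as one of the pre-specified outcomes.

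**The concern.** An outcome reported by randomized arm should be one that a child in either arm can reach on the same terms. Here a child must have received LR to be counted. If a child in the NS arm receives ceftriaxone and NS, never receives LR, and has a line clot, that clot is not an event. The same clot in a child in the LR arm who received LR and ceftriaxone is an event.

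Intravenous lines also clot for reasons unrelated to ceftriaxone and calcium. The definition does not require the two products to share a line or to be given close together, and it does not require evidence of precipitation. It therefore takes in ordinary clotting among LR recipients and leaves out ordinary clotting among children who received only NS. Without the second count there is no background rate against which to read the first.

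Two things are at stake. The arm totals could be read as a signal against LR that comes from the definition. And the pilot would not test whether line clotting can be captured in NS-arm children who receive no LR, although Section 6.3.4 sets out to assess the availability of data for each safety endpoint.

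**Working it through.** The documents give no rate or count for line clotting, so there is no figure of the plan's own to reproduce. The check has two parts: how a child in the NS arm can qualify, and how far the expected counts differ when true risk is equal.

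**Routes by which an NS-arm child can qualify**

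- *Before randomization.* Up to 40 mL/kg of crystalloid of any type is allowed (Section 3.4.1), and Section 5.4 sets no start time for LR receipt. This route is rare: Section 1.4 says more than 98% of comparable patients would start on NS.
- *Cross-over during the intervention phase.* Criterion 2 in Section 6.3.2 accepts 90% NS as adequate in the NS arm, so a child can meet it and still have received some LR.
- *After the intervention phase.* Assigned fluid stops at the end of the day after randomization, while the outcome window is four calendar days. If the day of randomization is day 0, two to four calendar days minus the one covered leaves days 2 to 4 (three days) of clinician-chosen fluid. If it is day 1, days 3 and 4 (two days) remain.

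The NS count is therefore forced to zero only if no NS-arm child receives LR by any of these routes.

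**Expected counts under equal true risk**

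Inputs:
- n = 35 per arm (Section 6.4).
- f = share given ceftriaxone: not in the documents; assumed 60%, range 30% to 90%.
- c = line-clot risk, the same in both arms: not in the documents; assumed 5%, range 2% to 10%.
- e = share of the arm that receives any LR: assumed 100% in the LR arm; 0, 10%, 25% and 50% in the NS arm.

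The 50% in Section 7.1.2 is a share of PICU resuscitation fluid. It is not a share of children, so e = 50% is an illustration and not an estimate.

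Formula: expected counted events = n × f × c × e.

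- LR arm: 35 × 0.60 × 0.05 × 1 = 1.05.
- NS arm, e = 0: 0.
- NS arm, e = 10%: 1.05 × 0.10 = 0.11.
- NS arm, e = 25%: 1.05 × 0.25 = 0.26.
- NS arm, e = 50%: 1.05 × 0.50 = 0.53.

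Over the assumed ranges, the LR-arm expectation runs from 35 × 0.30 × 0.02 = 0.21 to 35 × 0.90 × 0.10 = 3.15. In every case the NS-arm expectation is the fraction e of it, so the gap closes only when LR exposure is equal in the two arms.

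**Chance that nothing is seen**

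P(no LR-arm event) = (1 − f × c)^35 = 0.97^35 = 0.34. Over the assumed ranges it runs from 4% (f = 90%, c = 10%) to 81% (f = 30%, c = 2%).

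**Without the LR condition**

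Counted in all ceftriaxone recipients, the expectation is 1.05 in each arm (range 0.21 to 3.15). Counted in all randomized subjects with the same 5% risk, it is 35 × 0.05 = 1.75 in each arm.

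**The case against.** The best defence is that this outcome has a specific purpose. Sections 1.4 and 3.1.2 describe a labelled hazard: ceftriaxone can precipitate with calcium-containing fluid in the same line. NS contains no calcium and cannot cause it, so counting clots among co-exposed children is a legitimate exposure-specific listing. The pilot is not powered for safety, makes no formal comparison, and uses the count in no decision rule. Some clotting is also captured in both arms without a fluid condition: the Table 3 rows for treated central-line clots and deep venous thrombosis, and the thromboembolism item in Section 5.4.

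Much of this stands. It supports keeping the co-exposure listing, and it limits the importance for this study. It does not make the arm counts comparable. The definition covers any clot in any intravenous line, not precipitation, and Sections 6.3.4 and 8.1 present the endpoint as something to be viewed between groups. The central-line and thromboembolism items leave out peripheral lines and untreated clots, so they do not supply the missing NS comparator.

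A reader might infer something stronger: that an adherent NS arm can never have an event, or that an LR excess is certain to appear. The documents support neither. A child who received only NS throughout the intervention phase can receive LR later in the window, and an observed excess needs at least one LR-arm event. For the same reasons, a projection to the larger trial with zero NS-arm events would not be justified.

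**Conclusion.** The concern holds as a problem of comparability. Eligibility for the event depends on receipt of one randomized fluid. The expected count therefore leans toward LR under equal true risk whenever fewer NS-arm than LR-arm children receive LR. In the illustration this is 1.05 expected events against 0 to 0.53, with a 34% chance that the LR arm shows none. Those figures rest on assumed ceftriaxone use and clot risk and on every LR-arm child receiving LR; the direction of the bias does not depend on the particular rates.

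The consequence for this pilot is small. It matters more if the definition is carried into the larger trial, as Section 5.4 plans.

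A separate and lesser point is that Table 3 and Section 5.4 do not match. The footnoted row is limited to central lines and to clots that were treated with drugs. The Section 5.4 line-clot item has neither limit, and it adds the ceftriaxone and LR conditions. The row might instead be meant to map to the thromboembolism item, but the deep venous thrombosis and pulmonary embolus rows do not carry the footnote. The intended link is unclear.

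**What to change.** In Section 5.4, define the outcome as clotting of an intravenous line within four calendar days of randomization, in all randomized subjects, reported by randomized arm. Show ceftriaxone recipients as a subset by arm. Keep clots after co-exposure to ceftriaxone and LR as a descriptive listing, with the fluid actually given and its timing.

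The main count should not be restricted to ceftriaxone recipients. The study is open-label and staff are taught about the incompatibility (Section 3.1.2), so ceftriaxone use after randomization could differ by arm. The subset should be read with that caution.

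In Table 3, state which Section 5.4 outcome the footnoted central-line row refers to, and align the two definitions or remove the footnote.

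The cost is a short text change plus chart abstraction of line clotting for NS-arm subjects. Section 5.1.1 already collects fluids and medications for every subject but lists no line-clot field, so one would have to be added for both arms. No additional procedure on the child is needed.

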6 STATISTICAL CONSIDERATIONS

6.1 Primary Endpoint

The primary endpoint will be the proportion of total crystalloids administered as saline in each arm during the intervention phase (Aim 1).

6.2 Secondary Endpoints

Secondary endpoints will include the following:

- The proportion of total crystalloids administered as non-study fluid (i.e., cross-over) in each arm (Aim 1).
- The proportion of eligible patients treated in the pediatric ED who are enrolled, randomized, and treated with study fluid (Aim 2).
- The proportion of eligible patients who meet criteria for EFIC who are enrolled, randomized, and treated with study fluid *and* do not withdraw prior to completion of the follow-up phase.

6.3 Statistical Methods

6.3.1 Baseline Data

Baseline and demographic characteristics will be summarized by standard descriptive summaries (e.g. means and standard deviations for continuous variables such as age and percentages for categorical variables such as gender).

6.3.2 Feasibility Analysis

The primary analysis will be based on an intention-to-treat approach and will include all subjects randomized whether or not study fluid was administered.

The primary endpoint will be defined as meeting feasibility criteria if either of the following criteria are met:

- 3) There is an absolute difference in the mean use of NS between arms of at least 65% with a lower 95% CI border of >60%. For example, feasibility criteria would be met if 90% of crystalloid fluid in the NS arm was NS compared to only 25% in the LR arm. The proportion of NS use in each arm will be compared using the chi-squared test with a 95% bootstrap confidence interval with bias correction (assuming skewed distribution of data) around the difference in the proportion of NS use in each arm.
- 4) At least 85% of subjects in the NS arm receive $\geq 90\%$ of study fluid as NS during the study window *and* at least 80% of subjects in the LR arm receive $\geq 75\%$ of study fluid as LR.

The secondary endpoints will be defined as meeting feasibility criteria if:

- The mean proportion of total crystalloids administered as non-study fluid (i.e., cross-over) is $\leq 25\%$ in each arm (for example, $\leq 25\%$ of total crystalloid is administered as NS for patients randomized to the LR arm).
- The proportion of eligible patients treated in the pediatric ED who are enrolled, randomized, and treated with study fluid is $>65\%$.
- EFIC is approved by the IRB at CHOP
- The proportion of eligible patients who meet criteria for EFIC who are not enrolled or who are enrolled but withdraw prior to completion of the follow-up phase is $\leq 10\%$.

6.3.3 Efficacy Analysis

Efficacy endpoints will be tracked between groups as part of this pilot study, but no formal statistical comparisons will be undertaken due to insufficient statistical power. As part of our secondary feasibility analysis, however, we will determine the proportion of patients with complete data available for each efficacy endpoint listed in Section 5.3 to ensure that it is indeed feasible to capture the efficacy outcome measures planned for a subsequent large multicenter trial.

For subjects who may withdraw prior to death and prior to hospital discharge and for whom permission is not granted for continued follow-up of associated clinical efficacy outcomes, the National Death Index will be queried for survival status. According to FDA regulations, when a subject withdraws from a study, the data collected on the subject to the point of withdrawal remains part of the study database and may not be removed. If a subject withdraws from the interventional portion of a study and does not consent to continued follow-up of associated clinical outcome information, the investigator must not access for purposes related to the study the subject's medical record or other confidential records requiring the subject's consent. However, an investigator may review study data related to the subject collected prior to the subject's withdrawal from the study, and may consult public records, such as those establishing survival status

6.3.4 Safety Analysis

Safety endpoints will be tracked between groups as part of this pilot study, but no formal statistical comparisons will be undertaken due to insufficient statistical power. As part of our secondary feasibility analysis, however, we will determine the proportion of patients with complete data available for each safety endpoint listed in Section 5.5 to ensure that it is indeed feasible to capture the safety outcome measures planned for a subsequent large multicenter trial. Specifically, we will track laboratory testing performed as part of routine clinical practice in order to determine the frequency that laboratory results are available for the specified safety outcome measures listed in Section 5.4. It is notable that routine clinical practice for sepsis includes frequent (i.e., daily or more) measurement of blood lactate, sodium, potassium, chloride, and calcium.

6.4 Sample Size and Power

In a previous PECARN study called the FLUID trial (data not yet published), nearly 1400 pediatric patients presenting to the ED with diabetic ketoacidosis (DKA) were randomized to different fluid volumes and different fluid types (normal saline vs. half-normal saline).

We used FLUID data on adherence to fluid type assignment to simulate adherence in the proposed study, assuming that the LR arm will behave like the half-NS arm (i.e., the study intervention arm) and the NS arm will behave like the NS arm (i.e., the control arm) in the FLUID trial. In the FLUID trial, the mean percentage of correct fluid given was 96% in the NS arm and 91% in the half-NS arm. About 90% of subjects in the NS arm received at least 85% NS, while about 89% of those in the half-NS arm received at least 75% half-NS. Through simulation, by sampling from FLUID data, with 35 patients in each arm, the probability that at least 85% of subjects in the NS arm and 80% in the LR arm will receive the “adequate” amount of correct study fluids (i.e., $\geq 90\%$ of study fluid as NS in NS arm and $\geq 75\%$ of study fluid as LR in the LR arm) is approximately 80% (study power for criterion #2 of the Aim 1 feasibility analysis described in Section 6.3.2).

